1035 • Battery lifespan deficiency due to inadequate charging or extensive wireless
1036 communication
1037 • Intermittent device component disconnections/communication failures not leading to
1038 system replacement
1039 • Device issues clearly addressed in the user guide manual that do not require additional
1040 troubleshooting
1041 • Skin reactions from CGM sensor placement or pump infusion set placement that do not
1042 meet criteria for AE reporting

1043 **11.9 Timing of Event Reporting**

1044 • UADEs must be reported within 10 working days to the FDA after the sponsor first receives
1045 notice of the adverse effect.
1046 • Other reportable adverse events, device malfunctions (with or without an adverse event)
1047 and device complaints should be reported promptly, but there is no formal required
1048 reporting period.

CLINICAL PROTOCOL

- 1049 • The IDE Sponsor will investigate the UADE and if indicated, report the results of the
1050 investigation to the IRBs, FDA, and DSMB within 10 working days of the study team
1051 becoming aware of the UADE per 21CFR 812.46(b) (2).
- 1052 • The Medical Monitor will determine if the UADE presents an unreasonable risk to
1053 participants. If so, the DSMB must ensure that all investigations, or parts of investigations
1054 presenting that risk, are terminated as soon as possible but no later than 5 working days
1055 after the Medical Monitor makes this determination and no later than 15 working days after
1056 first receipt notice of the UADE.
- 1057 • In the case of a device system component malfunction (e.g. pump, CGM, control
1058 algorithm), information will be forwarded to the responsible manufacturer by the study
1059 personnel.

1060 **11.10 Stopping Criteria**

1061 **11.10.1 Participant Discontinuation**

1062 Rules for discontinuing study device use are described below.

- 1063 • The investigator believes it is unsafe for the participant to continue the intervention. This
1064 could be due to the development of a new medical condition or worsening of an existing
1065 condition; or participant behaviour contrary to the indications for use of the device that
1066 imposes on the participant's safety
- 1067 • The participant requests that the treatment be stopped
- 1068 • The participant tests positive for COVID-19 (during study testing or otherwise within 14
1069 days of study start) or subsequently develops symptoms for COVID-19 and tests positive.
- 1070 • Diagnosis of DKA. Any severe hypoglycemia event meeting the definition in section
1071 11.2.1 of the protocol.

1072 **11.10.2 Suspending/Stopping Overall Study**

1073 In the case of an unanticipated system malfunction resulting in a severe hypoglycemia or severe
1074 hyperglycemia event (as defined in section 11.2.2), use of the study device system will be
1075 suspended while the problem is diagnosed.

1076 In the event that two distinct episodes of DKA or two distinct severe hypoglycemia events as
1077 defined in section 11.2 occur, the overall study would be suspended while the underlying
1078 conditions are determined.

1079 In addition, study activities could be similarly suspended if the manufacturer of any constituent
1080 study device requires stoppage of device use for safety reasons (e.g. product recall). The affected
1081 study activities may resume if the underlying problem can be corrected by a protocol or system
1082 modification that will not invalidate the results obtained prior to suspension. The study Medical
1083 Monitor will review all adverse events and adverse device events that are reported during the study
1084 and will review compiled safety data at periodic intervals. The Medical Monitor may request
1085 suspension of study activities or stoppage of the study if deemed necessary based on the totality
1086 of safety data available.

CLINICAL PROTOCOL

1087 11.11 Independent Safety Oversight

1088 A Medical Monitor will review all DKA and severe hypoglycemia irrespective of relatedness to
1089 study device use, and all serious events (including UADEs) related to study device use at the time
1090 of occurrence. The Medical Monitor can request modifications to the study protocol or suspension
1091 or outright stoppage of the study if deemed necessary based on the totality of safety data available.
1092 Details regarding Medical Monitor review will be documented in a separate Medical Monitor
1093 document.

1094 11.12 Definition of a Data Breach

1095 A data breach is defined in the HITECH Act (43 USC 17932) as an unauthorized acquisition,
1096 access, or use of protected health information (PHI) that compromises the security or privacy of
1097 such information.

CLINICAL PROTOCOL

Chapter 12 Miscellaneous Considerations

12.1 Prohibited Medications, Treatments, and Procedures

Participants using glulisine at the time of enrollment will be asked to contact their personal physician to change their prescribed personal insulin to lispro or aspart for the duration of the trial.

The study devices (study insulin pump, study CGM) must be removed before Magnetic Resonance Imaging (MRI), Computed Tomography (CT) or diathermy treatment. Participants may continue in the trial after temporarily discontinuing use if requiring one of the treatments above.

12.2 Participant Withdrawal

Participation in the study is voluntary. Participant may withdraw at any time. For participants who do withdraw from the study, the study team will determine if their data will be used in analysis.

12.3 Confidentiality

For security and confidentiality purposes, subjects will be assigned an identifier that will be used instead of their name. Protected health information gathered for this study may be shared with the third-party collaborators. De-identified subject information may also be provided to collaborators involved in the study after the appropriate research agreement has been executed.

CLINICAL PROTOCOL

1113 Chapter 13 Statistical Consideration

1114 13.1 Design and Randomization

1115 The main study is itself an early exploratory study to assess glycemic responses of a fully closed-
1116 loop system (Rocket AP). This information is detailed in Table 1.

1117 Randomization will occur via selection from the above list using permuted blocks in groups of 4.

1118 13.1.1 Planned Analysis

1119 Our primary objective is to assess the impact of priming bolus on post prandial FCL control therefore we
1120 will test the following statistical hypotheses

1121

1122 **a. Null Hypothesis:** There is no difference in the means of time spent in the 70-180mg/dL range during
1123 daytime between FCL with and without prandial priming bolus (BPS at 6% and 0% of TDI respectively)

1124

1125 **b. Alternative Hypothesis:** There is a difference in the means of time spent in the 70-180mg/dL range during
1126 daytime between FCL with and without prandial priming bolus (BPS at 6% and 0% of TDI respectively)

1127

1128 To do so we will use repeated measure ANOVA models to predict daytime time in range with the BPS
1129 status a fixed effect and baseline HbA1c and gender as covariates.

1130

1131 *Secondary outcomes:*

1132 All secondary outcomes will be similarly analyzed. If an outcomes distribution is not suited for mixed
1133 model analysis (e.g. profound skewness, or large atom at boundary) we will perform paired Wilcoxon
1134 signed rank test (and loose the capacity to use covariate) to test difference in the median instead of the
1135 mean; this is expected for time below 70mg/dL, number of hypoglycemia, and possibly time above
1136 250mg/dL.

1137

1138 We do not plan to correct for multiple comparisons.

1139

1140 We do not expect substantial missing values in this highly supervised study, but if more than 3 subjects
1141 have one or more missing admissions, we will consider switching from RANOVA to mixed model repeated
1142 measures.

1143

CLINICAL PROTOCOL

1144 **13.2 Sample Size**

1145 As a early exploratory Study, the goal will be to complete up to 20 participants in the main study
1146 to provide data from a variety of individuals. This number was chosen out of feasibility and not
1147 from a formal power calculation. (The Pilot Study for this proposal will assess ease of system and
1148 will be completed in a minimum of 2-3 individuals prior to the beginning of the Main Study.) With
1149 N=20 and our randomized crossover design (allowing for paired comparison), we can hope to detect a
1150 minimum effect size of 0.66 at a power of 80%. Based of prior FCL study, the standard deviation of daytime
1151 TIR is approximately 12%, leading to a detectable difference in daytime TIR of 8%.

1152 **13.3 Outcome Measures**

1153 **13.3.1 Primary Efficacy Endpoint**

1154 The study design allows for multiple comparisons of blood glucose control during the study meals
1155 and exercise sessions, with for the primary comparison of interest being between the RocketAP
1156 with and without BPS. Our primary endpoint is CGM time-in-range 70-180 mg/dL for the daytime
1157 period 6 am – 12 am when on each treatment modality (BPS vs. no BPS).

1158 **13.3.2 Secondary Outcomes**

1159 Each admission is separated into windows of analysis:

- 1160 • The entirety of the admission (24h: 4pm to 4pm)
- 1161 • The 4 hours following each of the meals.
- 1162 • The overnight period (12 am to 6 am)

1163 For each of these periods we will compute the following outcomes:

- 1164 • Number of hypoglycemia events defined as at least two consecutive CGM values
1165 <70mg/dL or a hypoglycemia treatment (two events separated by less than 30 minutes are
1166 counted as one).
- 1167 • Percent CGM time <70 mg/dL
- 1168 • Percent CGM time between 80-140mg/dL
- 1169 • Percent CGM time between 70-180mg/dL
- 1170 • Percent CGM time >180 mg/dL
- 1171 • Percent CGM time >250 mg/dL
- 1172 • Units of insulin injected
- 1173 • Area under the curve when accounting for starting BG
- 1174 • Low Blood Glucose Index
- 1175 • High Blood Glucose Index
- 1176 • CGM coefficient of variation
- 1177 • Mean CGM

CLINICAL PROTOCOL

1179

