Investigational Device	UVA Model Predictive Control Artificial Pancreas (RocketAP) with and without use of the Bolus Priming System (BPS)
Objectives	The purpose of this study is to show the safety and feasibility of a new fully automated AP controller with and without the Bolus Priming System
Study Design	A randomized cross-over trial assessing glycemic responses to a fully automated AP system using two approaches: 1) using the Bolus Priming System (which detects shifts in glucose level to trigger a priming dose of insulin) 2) without the Bolus Priming System We will also have structured meal and exercise challenges of the fully closed loop system.
Number of Sites	One
Endpoint	The primary outcome will be time in range 70-180 mg/dL for a 24-hour period.
Population	Key Inclusion Criteria 
• Age 18 and \leq65 years of age• Clinical diagnosis, based on investigator assessment, of type 1 diabetes for at least one year• Currently using insulin for at least six months• Currently using insulin pump for at least three months
Sample Size	
• Pilot Study: complete a minimum of 2-3 participants• Main Study: complete up to 20 participants
Treatment Groups	Randomized crossover: Participants will be randomized to the order that they experience the use of the BPS in fully automated closed loop (FCL) (for 24 hours each, with a 24-hour washout in between): 1) with the BPS active, 2) without BPS.
Participant Duration	Pilot Study: Participants will be admitted to a local hotel or rental house for up to approximately 24 hours and will have a dinner with the RocketAP without the BPS Main Study: Participants will be admitted to a local hotel for approximately 96 hours.

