152 completing a minimum of 2-3 participants. This admission will be about 24 hours at a hotel/rented
153 house. Enrollment in the Main Study will proceed with the goal of completing 20 participants.

154 **1.3.1 Study Hardware/Software**

155 The study itself will involve use of the DiAs prototyping platform (MAF 2109), connected to a
156 Tandem t:AP research pump and a Dexcom G6 sensor, and implementing RocketAP with and
157 without BPS. Upon arrival at the hotel, participants will be instructed in how to use the Tandem
158 research pump as well as the UVa AP system, including stopping the system.

159 **1.3.2 Timing of UVa Artificial Pancreas Use**

[figure not shown]
160 The participants will arrive to hotel the evening before starting the experimental system to allow
161 for a settling of blood glucose in an unfamiliar environment. The next morning, participants will
162 be connected to a Tandem research pump connected to the UVa DiAs platform and their Dexcom

CLINICAL PROTOCOL

163 G6 Transmitter will be linked with DiAs. Participants will then be taught how to use DiAs in this
164 configuration. The research pump will be programmed with the individual's usual insulin
165 parameters. Once started, the participants will have their blood sugar managed through this system
166 during the entirety of the time at hotel.

167 1.3.3 Study Controller Sessions

168 *Order and timing of controller sessions:* During the hotel stay, participants will have two separate
169 24-hour periods during which they will receive FCL control with and without the BPS active.
170 These will be separated by a 24-hour challenge period which will involve further challenges. The
171 timing and potential order of these sessions is shown in Figure 1.

[figure not shown]

172

173 Figure 1: Timeline and randomized order of the Study Controller Sessions

174 During these 24-hour periods participants will be followed for the experimental meals as part of
175 the Study Controller Sessions to compare blood glucose control with and without the BPS (Figure
176 1). The study meals and activities will be standardized between study sessions (see Figure 2).

CLINICAL PROTOCOL

177

178 Figure 2: Timeline of Study Controller Sessions and Study Meals and activities. There will be two identical 24-
179 hour periods (FCL1 in green and FCL2 in orange), separated by a 24-hour challenge period (FCL1 in green-hatched)

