640 by study staff. During FCL1 and FCL2, participants will do a mild to moderate walking or similar
641 exercise at approximately 4pm on each of those study days.

642 During the challenge phase (the 24-hour period between the FCL1 and FCL2), participants will
643 undergo supervised session of high-intensity interval training (HIIT). The HIIT workout will
644 consist of a 5-minute low intensity warmup period, a workout of about 1 minute of vigorous
645 exercise followed by approximately 2 minutes of light intensity exercise or rest. This 3-minute set
646 of intervals may be repeated up to 6 times or until volitional exhaustion, followed by approximately
647 5 minutes of light intensity cooldown and stretching. The goal of this will be to assess the safety
648 of the AP system in HIIT, given that HIIT has been observed to result in an increase in BG levels,
649 which could theoretically lead to activation of the BPS—dosing insulin. The AP system will be
650 monitored for BPS activation during this workout. If the BPS is activated, participants will
651 continue to be monitored for BG excursions, including receiving treatment for hypoglycemia if
652 this occurs (as described in the Glycemic Treatment Guidelines).

653 Exercise challenges will be terminated early with subjective symptoms such as shortness of breath,
654 chest pain, dizziness, palpitations, or any such concerning symptoms reported by participants.
655 Participants will stop their participation in the exercise portion of the study if reporting any
656 concerning symptoms. Study physicians (or physician's assistants) will assess the participants for
657 their need for additional care outside the study. If symptoms resolve entirely and there is no
658 additional requirement for care outside the study, participants will stop participation in the exercise
659 portion of the study and will not repeat that portion of the study. Participants however may then
660 continue with the remainder of the study per investigator discretion.

661 Participants will also be free to engage in low-intensity activity (i.e. walking) during the hotel
662 admission but will be asked to have this match between 24-hour study periods as best as possible.
663 Participants may leave the hotel to be outside, provided they are accompanied by a study staff
664 member and follow COVID precautions in place at the time of study, as described in Section .3.
665 Participants will enjoy quiet activities in the evening.

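### The primary crossover model has no period term, although FCL2 always follows the exercise and meal-challenge day and FCL1 never does; a period shift costs power and, with unequal sequences, biases the BPS estimate.

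*Combined protocol and SAP*

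**What the plan says.** Section 13.1.1 gives the whole primary model: "To do so we will use repeated measure ANOVA models to predict daytime time in range with the BPS" "status a fixed effect and baseline HbA1c and gender as covariates". The mixed-model fallback for missing admissions adds no terms. Secondary outcomes with unsuitable distributions go to a paired Wilcoxon signed-rank test without covariates.

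The Treatment Groups row of the protocol summary describes the two conditions as given "for 24 hours each, with a 24-hour washout in between". Section 7.7 shows what fills that interval: "During the challenge phase (the 24-hour period between the FCL1 and FCL2), participants will" do a supervised high-intensity interval session. Section 7.6 adds a high-carbohydrate, high-fat dinner and an early breakfast of fast-acting carbohydrate, on that day only. Closed loop runs throughout. Before FCL1 the situation is different. Section 1.3.2 says "The participants will arrive to hotel the evening before starting the experimental system to allow" glucose to settle, and Section 1.3.3 has participants on their home management until the study system starts.

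Section 13.2 supports the sample size with a paired calculation: "N=20 and our randomized crossover design (allowing for paired comparison), we can hope to detect a" "minimum effect size of 0.66 at a power of 80" per cent. It then uses an SD of about 12 points to reach a detectable difference of 8 points.

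**The concern.** In a two-period crossover each participant's BPS-minus-no-BPS difference contains the BPS effect plus or minus any shift between periods. The sign depends on the order received. HbA1c and gender, entered as main effects, are the same in both of a participant's periods, so with both periods observed they cannot change the within-participant contrast. Period is the term that can, and it is missing.

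A shift is plausible here because the run-in to each period is fixed and different. FCL1 follows a home-managed evening and includes the first hours on a new system. FCL2 follows a day of closed loop with hard exercise and unusual meals. Matching meals and activity within FCL1 and FCL2 does not equalise what came before them.

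With equal sequences, the shift inflates the residual, widens the interval and makes the test conservative. With unequal sequences, part of the shift is reported as a BPS effect. Lost power matters particularly here: Section 1.1 hypothesises that control without BPS will be similar, and a non-significant result could be read as support for that.

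**Working it through.** **Inputs.** N=20, effect size 0.66, power 80% and SD 12 points come from Section 13.2. The two-sided alternative comes from Section 13.1.1 ("There is a difference in the means of time spent in the 70-180mg/dL range during" daytime). Two sequences in permuted blocks of 4 (Section 4.2) give 10:10 if all 20 complete. Three things are assumed: alpha 0.05, SD 12 as the SD of the paired difference, and a period shift P (FCL2 minus FCL1) of 0 to 12 points.

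**The plan's figure.** A paired t-test with N=20, 19 df and two-sided 0.05 has 79.9% power at 0.66, and the 80% detectable effect is 0.660. Then 0.66 × 12 = 7.92, rounded to 8. The stated figure is reproduced, and it is a paired test with no period term.

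**Model.** For BPS first, d = τ − P + e. For BPS second, d = τ + P + e. SD(e) = 12 and τ = 7.92.

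- *Without a period term:* one-sample t on d, 19 df. At 10:10 the residual sum of squares divided by 144 is noncentral chi-square with noncentrality 20P²/144, so the apparent SD is √(144 + 20P²/19). For P=8 this is √211.4 = 14.5.
- *With a period term:* the estimate is the average of the two sequence means, on 18 df. P cancels.

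**Results at 10:10:**

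| Shift P (points) | Apparent SD | Power, no term | Type I error, no term | Power, with term |
|---|---|---|---|---|
| 0 | 12.0 | 79.9% | 5.0% | 79.7% |
| 2 | 12.2 | 79.1% | 4.7% | 79.7% |
| 4 | 12.7 | 76.6% | 3.9% | 79.7% |
| 6 | 13.5 | 72.2% | 2.9% | 79.7% |
| 8 | 14.5 | 66.1% | 1.9% | 79.7% |
| 12 | 17.2 | 49.4% | 0.6% | 79.7% |

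These come from numerical integration. Simulation with 200,000 replicates agrees at P = 0, 4 and 8. Without the term, the 80% detectable difference rises from 7.9 points (no shift) to 8.3, 9.1 and 10.4 for shifts of 4, 8 and 12. With the term it is 7.95 throughout.

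**Unequal completers.** Without the term, bias = P × (number BPS second − number BPS first)/N. At 12:8 and P=8, the size is 8 × 4/20 = 1.6 points. At P=4 it is 0.8. At 11:9 the sizes are 0.8 and 0.4. For P=8:

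| BPS first : BPS second | Bias, no term | Power, no term | Power, with term (bias 0) |
|---|---|---|---|
| 11:9 | −0.8 | 55.7% | 79.3% |
| 9:11 | +0.8 | 75.7% | 79.3% |
| 12:8 | −1.6 | 45.1% | 78.1% |
| 8:12 | +1.6 | 83.8% | 78.1% |

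**If 12 is the SD of TIR itself.** The SD of the difference is then 12√(2(1−ρ)), where ρ is the within-participant correlation; ρ=0.5 returns 12. At a true difference of 8 points, a shift of 8 lowers unadjusted power from 66.7% to 55.0% at ρ=0.3, from 80.7% to 67.2% at ρ=0.5, and from 95.4% to 84.3% at ρ=0.7. With the term, power is 66.4%, 80.5% and 95.3%.

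**The case against.** The strongest reply is that the harm is conditional. The documents give no size for a period shift. At 2 points the loss is under one percentage point of power, and below about 1.1 points the lost degree of freedom outweighs the gain at 10:10. Order is randomised, meals and activities are matched, a settling evening precedes FCL1, and blocks of 4 divide 20 exactly. With balanced completers the estimate is unbiased and false positives are not inflated. A 12:8 split needs lopsided dropout. The trial is also labelled exploratory, with N set by feasibility. All of this stands as a limit on size, but none of it is a reason to omit the term.

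Imbalance is possible. The target is up to 20 completers; replacement of dropouts is optional and not tied to a sequence (Section 4.2); a participant cancelled at check-in is not replaced (Section 7.4); and the 80% CGM rule (Section 13.3.4) can remove a period.

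Three technical points also stand. The term's cost is not always 0.2 points of power: at 12:8 with no shift it is 79.9 − 78.1 = 1.8 points. A sequence term, like HbA1c, does not change the BPS contrast when pairs are complete. And a period term removes only a shift common to both orders. Section 1.3.3 has the challenge day start on the FCL1 assignment, so an after-effect that differs by order would remain.

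**Conclusion.** The concern holds. The model omits period in a design whose periods have different, fixed antecedents. At 10:10 the cost is precision: for assumed shifts of 4 to 8 points, power falls from 79.9% to between 76.6% and 66.1%, and the test runs at 3.9% to 1.9% rather than 5%. At 11:9 or 12:8 the same shifts bias the estimate by 0.4 to 1.6 points, in a direction set by which sequence is larger; the rejection rate can then rise as well as fall. These sizes rest on SD 12 for the paired difference, two-sided alpha 0.05, an additive shift and no carryover. The omission itself is certain; the size of the harm depends on a shift the documents do not quantify. The change should be made, because it protects against a foreseeable effect at almost no cost. Adding the term after the data are seen would be a post hoc choice.

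**What to change.** In Section 13.1.1, specify daytime TIR with fixed effects for BPS status, period (FCL1 or FCL2) and sequence, and participant as a random effect. HbA1c and gender may stay. Use the same terms in the missing-data fallback. Period does the work; sequence is conventional and takes no within-participant degree of freedom.

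For outcomes moved to a rank test, replace the signed-rank test with a rank-sum test comparing FCL1-minus-FCL2 differences between the two randomised sequences. With no BPS effect and no carryover, those differences have the same distribution in both sequences whatever the period effect, so the test does not rely on an additive shift. Its power was not computed here.

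State that treatment-specific carryover is not addressed by this model, and do not describe the challenge day as a washout without that qualification.

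The cost is a sentence or two of SAP text and one within-participant degree of freedom (19 to 18). With no shift, that is about 0.2 points of power at 10:10 and 1.8 at 12:8. No new data or participants are needed.

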122 During the washout period between FCL1 and FCL2, we will test the RocketAP system in FCL
123 with further challenges, both before and after the change in BPS treatment arm—i.e., not as a
124 cross-over assessment but a comparison between participants randomized to start with or without
125 BPS. These challenges will include:

126 • A session of high-intensity interval training (assessing the safety of the BPS when BG's
127 may spike during bursts of anaerobic activity)

CLINICAL PROTOCOL

- 128 • A high-carbohydrate, high-fat meal (assessing how the system responds to prolonged
129 carbohydrate absorption)
- 130 • Ingestion of a bolus of simple sugar (assessing the safety of the BPS when the user's
131 blood sugar spikes from a relatively low amount of carbohydrate)

132 Participants will be admitted to a hotel and started on the RocketAP for the purpose of comparing
133 FCL use with and without BPS as described above, all implemented on the DiAs platform (MAF
134 2109). As an assessment of the efficacy of the system in maintaining BG control, participants will
135 be followed for approximately 24 hours in the randomized phase (FCL1 vs. FCL2) and during the
136 24-hour cross-over phase. Our primary outcome will be one of efficacy in assessing BG control
137 (TIR 70-180 mg/dL) between the two 24-hour FCL1/FCL2 periods.

138 We hypothesize that performances of RocketAP without BPS in FCL will provide similar glycemic
139 control as FCL with BPS. We expect that this will constitute an important step toward having a
140 fully automated AP system because it may remove the need for a BPS system that itself could
141 increase risk of episodes of hypoglycemia.

142 **1.2 Study Objective**

143 The purpose of this study is to test the performance of the RocketAP in FCL both with and without
144 the BPS, assessing efficacy and safety. We will target completion of up to 20 adults in a
145 randomized cross-over trial, comparing blood glucose time in range 70-180 mg/dL for two 24-
146 hour periods and assessing TIR during an additional challenge period, which will be compared
147 between those who started on BPS vs. those who did not.

148 **1.3 Study Design**

149 We will consent up to 30 participants, ages ≥ 18.0 and ≤ 65 years, with a goal to have up to 20
150 participants complete the trial. The study will be performed overnight at a local hotel/rental house
151 (heretofore referred to as "hotel"). Enrollment in the Pilot Study will proceed with the goal of

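### Does the 8-point detectable difference in Section 13.2 rest on the wrong standard deviation?

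*Combined protocol and SAP*

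**What the plan says.** Section 13.2 says of the target of up to 20 completers: "This number was chosen out of feasibility and not" from a power calculation. It then offers a sensitivity statement. With "N=20 and our randomized crossover design (allowing for paired comparison), we can hope to detect a" "minimum effect size of 0.66 at a power of 80%. Based of prior FCL study, the standard deviation of daytime" "TIR is approximately 12%, leading to a detectable difference in daytime TIR of 8" per cent.

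The setting for that statement is elsewhere in the document:

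- Section 13.1.1 tests a null of no difference in mean daytime TIR against a two-sided alternative: "There is a difference in the means of time spent in the 70-180mg/dL range during" daytime. The analysis is a repeated-measures ANOVA with Bolus Priming System (BPS) status as a fixed effect and baseline HbA1c and gender as covariates.
- Section 1.1 states the investigators' expectation: "We hypothesize that performances of RocketAP without BPS in FCL will provide similar glycemic" control to the system with BPS.

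No alpha, within-person correlation or explicitly labelled SD of paired differences appears in the documents.

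**The concern.** A standardised effect from a paired test must be multiplied by the SD of the within-person differences to give a difference in the original units. Section 13.2 ties its 0.66 to the paired comparison and then multiplies it by a quantity worded as the SD of the outcome. These are different quantities unless the within-person correlation happens to be about 0.5. Read literally, the step mixes units, and the 8 points could be off in either direction.

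The stake is how a null result is read. The investigators expect the two modes to perform similarly, but the plan tests for a difference and sets no equivalence or non-inferiority margin. A reader of a non-significant result might use the 8 points to judge what the trial could have missed. If the real detectable difference were 11 points, that reading would be too reassuring. If it were 6, the trial would be more sensitive than it claims.

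**Working it through.** **Inputs.** From Section 13.2: N=20, paired comparison, 80% power, effect size 0.66, SD 12%, detectable difference 8%. From Section 13.1.1: a two-sided alternative. Assumed: alpha 0.05, which the documents do not state.

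**1. Reproduce 0.66.** For a paired t-test, power = P(|T| > t(0.975, 19)), where T is noncentral t with 19 df and noncentrality d x sqrt(20).

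- At d = 0.66 the noncentrality is 0.66 x 4.472 = 2.95 and the power is 79.9%.
- Solving for exactly 80% gives d = 0.6604.
- Using 18 df, as in a crossover analysis that also fits period, gives 0.662.

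The alternatives do not fit: one-sided 0.05 gives 0.577, the two-sided normal approximation 0.626, and a two-sample t-test 0.909 (20 per group) or 1.325 (10 per group). So 0.66 is the two-sided paired figure, in units of the SD of differences.

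**2. Reproduce 8%.** 0.66 x 12 = 7.92, which rounds to 8. The multiplication is correct.

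**3. If 12% is the SD of paired differences.** The 8 points then stands as written. Power for a true 8-point difference (d = 8/12 = 0.667) is 81%.

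**4. If 12% is the SD within each session.** Assume equal session SDs and within-person correlation rho. Then SD of differences = 12 x sqrt(2(1 - rho)), and detectable difference = 0.6604 x that SD. The rho values are assumptions; none is in the documents.

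| rho (assumed) | SD of differences | Detectable difference (points) | Power for 8 points |
|---|---|---|---|
| 0 | 16.97 | 11.2 | 52% |
| 0.3 | 14.20 | 9.4 | 67% |
| 0.4 | 13.15 | 8.7 | 73% |
| 0.5 | 12.00 | 7.9 | 81% |
| 0.6 | 10.73 | 7.1 | 88% |
| 0.7 | 9.30 | 6.1 | 95% |
| 0.9 | 5.37 | 3.5 | over 99% |

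**5. Where does the result still round to 8?** Results of 7.5 to 8.5 need an SD of differences from 7.5/0.6604 = 11.36 to 8.5/0.6604 = 12.87. With rho = 1 - SD²/288, that is rho from 0.55 down to 0.42.

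**6. Unequal session SDs.** With assumed SDs of 10% and 14% and rho 0.5, the SD of differences is sqrt(100 + 196 - 140) = 12.49 and the detectable difference is 0.6604 x 12.49 = 8.25 points, so little changes.

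**7. What the finished trial will supply.** The 95% confidence interval for the mean difference has half-width t(0.975, 19) x SD of differences / sqrt(20). At an SD of 12 this is 2.093 x 12 / 4.472 = 5.6 points. In the report the observed SD takes the place of the planning value, so the ambiguity in Section 13.2 does not carry through.

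**The case for a change.** The strongest case for a change is that the plan chose to publish a figure in TIR points, that the figure cannot be traced from the text, and that a clarification would take only a few words. The trial hopes to show similarity without setting a margin, so a reader has some reason to look at the 8 points. If 12% is a per-session SD and the correlation is low, a true 8-point loss would be missed about half the time.

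The unit mismatch in the wording stands, and so does the absence of a stated alpha. The rest carries less weight. The 12% comes from a prior study that the reader cannot see, and it follows directly on a sentence about paired comparison, so shorthand for the SD of differences is a natural reading. The low-power case needs a correlation near zero between two sessions in the same person, which is an extreme assumption. Between 0.4 and 0.6 the detectable difference stays within about a point of 8.

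The opposite argument, that the crossover makes 8 points conservative because "The study meals and activities will be standardized between study sessions (see Figure 2", does not settle the matter either. Standardising the days could reduce between-person or day-to-day variation, so it does not place the correlation on either side of 0.5.

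**Conclusion.** The concern identifies a real ambiguity in wording but does not show an error. The standardised figure of 0.66 is correct for 20 completers at two-sided alpha 0.05, whatever the 12% means. Its conversion to 8 points is right if 12% is the SD of paired differences, or if session SDs are 12% and the correlation is about 0.42 to 0.55. Outside those conditions it is too low or too high: 9.4 points at an assumed correlation of 0.3, and 6.1 at 0.7. The documents cannot decide between these readings.

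No change follows, because nothing in the trial depends on the answer. The sample size was set by feasibility, the study is described as early and exploratory, and the statement is framed as a hope. The hypotheses, primary analysis and endpoint are the same under every reading. Analysts with access to the prior closed-loop data can tell which SD the 12% is, and a null result will properly be read from the observed paired differences and their confidence interval. This is missing detail in a supporting sentence.
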